7.2.1.2.5 Worsening of Underlying Disease and/or Other Pre-Existing Conditions

Worsening of the underlying disease and/or of other pre-existing conditions will be recorded as an AE/SAE in the eCRF.

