7.2.1.3 Adverse Event and Serious Adverse Event Reporting

All AEs, serious and non-serious, occurring during the course of the clinical trial (i.e., from signing the informed consent through the follow-up period) will be collected, documented, and reported to the sponsor by the investigator on the appropriate eCRF and SAE reporting forms.

For each AE, the investigator will provide the onset date, end date, seriousness, grade, relatedness, treatment required, outcome, and action taken with the study agent. The investigator will determine the grade as defined in [Section 7.2.1.2.3](#) and the causal relationship to the study agent (relatedness) as defined in [Section 7.2.1.2.4](#).

The investigator must report the following events immediately (within 24 hours or the next business day whichever is shorter) to the sponsor or designee (refer to the Lab Manual/ISF for specific instructions): SAEs and non-serious AEs relevant to the reported SAE and protocol-specified AESI.

The investigator does not need to actively monitor subjects for adverse events once the clinical trial has ended. However, if the investigator becomes aware of an SAE(s) that occurred after the subject has completed the clinical trial, it should be reported by the investigator to the sponsor if considered relevant by the investigator.

Any AE occurring during the study must be documented in the subject's medical records and as an AE in the eCRF. Any SAE occurring during the study must be documented in the subject's medical records and as an SAE in the eCRF.

A separate SAE report should be used for each SAE. However, if at the time of initial reporting, multiple SAEs are present that are temporally and/or clinically related, they may be reported on the same SAE report.

The investigator should attempt to establish a diagnosis of the event (that meets the definition of an AE or SAE) based on signs, symptoms, and/or other clinical information. In such cases, the diagnosis should be documented as the AE and/or SAE and not the individual signs or symptoms. The diagnosis will become the basis for the verbatim term as reported by the investigator. If no diagnosis is known and clinical signs and symptoms are not present, the abnormal finding should be recorded.

The investigator will take all appropriate and necessary therapeutic measures required for resolution of the AE. Any medication necessary for the treatment of an AE must be recorded on the concomitant medication case report form.

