The Kenward-Roger method will be used to determine denominator degrees of freedom. An unstructured variance-covariance matrix will be used for the above repeated measures model. If the model does not converge using the unstructured matrix, the first order autoregressive structure and the compound symmetry structure will be employed, in that order.

The above analyses will be repeated on the PP set as a sensitivity analysis.

Additionally, the number of subjects with change from baseline in BCVA letter score for the following categories will be summarized with counts and percentages:

- ≥ 15 letters;
- ≥ 14 and ≥ 10 letters;
- ≥ 9 and ≥ 5 letters;
- ≥ 4 and ≥ -4 letters;
- ≥ -5 and ≥ -9 letters;
- ≥ -10 and ≥ -14 letters;
- ≤ -15 letters.

BCVA results will also be presented in a data listing. BCVA results in the fellow eye are not included in the analyses but will be included in the listings. BCVA will also be summarized by visit using box plots.

15. Analysis of the Secondary Endpoints

The analyses for secondary endpoints (incidence, seriousness and severity of AEs) will be discussed in the next section as part of the safety analyses. There is no secondary efficacy endpoint for the study.

16. Safety Analyses

Safety will be assessed for the following endpoints using the Safety set:

- Incidence, seriousness, and severity of AEs;
- Observed slit-lamp biomicroscopy values;
- Observed intraocular pressure (IOP) values;
- Changes from baseline in clinical laboratory values;
- Changes from baseline in physical examination;
- Changes from baseline in vital signs.

Adverse events will be presented using frequencies and percentages of subjects.

Other safety endpoints including slit-lamp biomicroscopy, IOP, clinical laboratory values, physical examination, and vital signs will be summarized using descriptive statistics. Changes or shifts from baseline will also be summarized where appropriate. Assessments performed by eye (study eye and fellow eye) will be summarized separately. No statistical inferential testing will be performed for safety variables.

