16.1 Adverse Events

AEs are defined as any untoward medical occurrence associated with the use of an IMP in humans, whether or not considered IMP-related. All AEs, serious and non-serious, occurring during the course of the clinical trial (i.e., from signing the informed consent through the follow-up period) will be collected, documented, and reported. All AEs that occur or worsen on or after the first use of IMP will be considered as treatment-emergent AEs (TEAE). Reported AEs that begin prior to the first dose of IMP are classified as non-TEAEs; these will only be included in subject listings and not included in summary tables.

When reporting an AE, the event description should use the best matching terminology describing the event as found in the Common Terminology Criteria for Adverse Events (CTCAE v4.03). Standardized terms from the CTCAE will be used to categorize events for reporting to regulatory authorities using the Medical Dictionary for Regulatory Activities (MedDRA, v. 21.0).

The severity of all reported AEs are graded by the investigator into one of the following five (5) CTCAE categories:

- Grade 1 (Mild)
- Grade 2 (Moderate)
- Grade 3 (Severe)
- Grade 4 (Life-Threatening)
- Grade 5 (Death)

The relatedness of IMP to AE will be classified as definite, possibly, or unrelated. Documentation of AEs will include start date, end date, seriousness, severity, relatedness, whether or not medication was required, outcome, and action taken with the study agent.

A serious adverse event (SAE) is defined for this protocol as any AE that meets one or more of the following criteria:

- A death (CTCAE Grade 5 event) occurring during the study, whether or not considered treatment-related;
- A life-threatening event (CTCAE Grade 4);

- An event requiring inpatient hospitalization or prolonged hospitalization due to the adverse event;
- An adverse event resulting in a significant, persistent, or permanent change, impairment, damage or disruption in the participant's body function or structure, physical activities or quality of life;
- An event that otherwise required a medical or surgical intervention to preclude permanent impairment or damage (excluding unrelated elective or cosmetic procedures).

An AE of special interest (AESI) is defined for this protocol as any the following outcomes:

- Hepatic injury defined by the following alterations of liver parameters:

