 - For subjects with normal liver function at baseline an elevation of aspartate aminotransferase (AST) and/or alanine aminotransferase (ALT) \geq 3-fold the upper limit of normal (ULN) combined with an elevation of total bilirubin \geq 2-fold the ULN measured in the same blood draw sample;
- Abrupt decrease of BCVA ($>$ 15 letters lost from baseline);
- QTc interval prolongation ($>$ +50 ms from baseline and $>$ 450 ms).

An overall tabular summary of TEAEs will be presented that includes the number and percentage of subjects who experienced at least one TEAE. These summaries will also include breakdowns of TEAEs further categorized as ocular or non-ocular, and within these categories as drug-related TEAEs, TEAEs with CTCAE Grade 3/4/5, drug-related TEAEs with CTCAE Grade 3/4/5, TEAEs with an outcome of death, serious TEAEs, drug-related serious TEAEs, TEAEs leading to discontinuation of IMP and drug-related TEAEs leading to discontinuation of IMP.

Furthermore, the number and percentage of subjects with TEAEs by SOC and PT; by SOC, PT and maximal severity; by SOC and PT for TEAEs; by SOC and PT for SAEs; and by SOC and PT for TEAEs leading to subject withdrawal will be presented. Separate summaries will be provided for ocular and non-ocular TEAEs (including systemic). Adverse events of special interest will also be summarized by SOC and PT. These summaries by SOC and PT will be at the subject level. If a subject reports the same PT multiple times within the same SOC, that PT will only be counted once within that SOC. As with the PT, if a subject reports multiple conditions within the same SOC, that SOC will only be counted once.

All AEs (including non-TEAEs) will also be presented in subject listings.

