14.2.7.2	Presence of Leakage from Choroidal Neovascularization as Demonstrated by Fluorescein Angiography in the Study Eye at Scheduled Visits	PP Set
14.2.7.3	Summary of Size of Leakage from Choroidal Neovascularization (Number of Disc Areas) and Change from Baseline as Demonstrated by Fluorescein Angiography in the Study Eye at Scheduled Visits	Evaluable Set
14.2.7.4	Summary of Size of Leakage from Choroidal Neovascularization (Number of Disc Areas) and Change from Baseline as Demonstrated by Fluorescein Angiography in the Study Eye at Scheduled Visits	PP Set
Safety Analyses		
14.3.1.1	Overall Summary of Treatment-Emergent Adverse Events	Safety Set
14.3.2.1	Summary of All Ocular Treatment-Emergent Adverse Events by System Organ Class and Preferred Term	Safety Set
14.3.2.2	Summary of All Non-Ocular Treatment-Emergent Adverse Events by System Organ Class and Preferred Term	Safety Set

Table Number	Title	Set
14.3.3.1	Summary of All Ocular Treatment-Emergent Adverse Events Suspected to be Related to Investigational Medicinal Product by System Organ Class and Preferred Term	Safety Set
14.3.3.2	Summary of All Non-Ocular Treatment-Emergent Adverse Events Suspected to be Related to Investigational Medicinal Product by System Organ Class and Preferred Term	Safety Set
14.3.4.1	Summary of All Ocular Serious Treatment-Emergent Adverse Events by System Organ Class and Preferred Term	Safety Set
14.3.4.2	Summary of All Non-Ocular Serious Treatment-Emergent Adverse Events by System Organ Class and Preferred Term	Safety Set
14.3.5	Summary of All Adverse Events of Special Interest by System Organ Class and Preferred Term	Safety Set
14.3.6.1	Summary of All Ocular Treatment-Emergent Adverse Events Leading to Subject Withdrawal by System Organ Class and Preferred Term	Safety Set
14.3.6.2	Summary of All Non-Ocular Treatment-Emergent Adverse Events Leading to Subject Withdrawal by System Organ Class and Preferred Term	Safety Set
14.3.7.1	Summary of Ocular Treatment-Emergent Adverse Events by Maximum Severity, System Organ Class and Preferred Term	Safety Set
14.3.7.2	Summary of Non-Ocular Treatment-Emergent Adverse Events by Maximum Severity, System Organ Class and Preferred Term	Safety Set
14.3.8.1	Summary of Slit Lamp Biomicroscopy	Safety Set
14.3.8.2.1	Shift in Overall Results of Slit Lamp Biomicroscopy	Safety Set
14.3.8.2.2	Shift in Slit Lamp Biomicroscopy Anterior and Vitreous Chamber	Safety Set

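### The ocular TEAE tables do not separate study-eye from fellow-eye events, although slit lamp and IOP are shown by eye

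*SAP*

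**What the plan says.** **Division of adverse events.** SAP 16.1 states "Separate summaries will be provided for ocular and non-ocular TEAEs (including systemic". Counting is by subject: "If a subject reports the same PT multiple times within the same SOC, that PT will only be counted once within that SOC". The table list in SAP 24 follows this, with titles such as "Summary of All Ocular Treatment-Emergent Adverse Events by System Organ Class and Preferred Term" (14.3.2.1). The titles of 14.3.3.1 (suspected related), 14.3.4.1 (serious), 14.3.6.1 (leading to withdrawal) and 14.3.7.1 (maximum severity) name no eye either. The AESI for abrupt BCVA loss (Protocol 7.2.1.2.7, SAP 16.1) and its table, 14.3.5, also name no eye.

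**AE data items.** SAP 16.1: "Documentation of AEs will include start date, end date, seriousness, severity, relatedness, whether or not medication was required, outcome, and action taken". Protocol 7.2.1.3: "the investigator will provide the onset date, end date, seriousness, grade, relatedness, treatment required, outcome, and action taken with the study agent". Neither list mentions the eye.

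**By-eye convention elsewhere.** SAP 16 says "Assessments performed by eye (study eye and fellow eye) will be summarized separately". SAP 16.2 and 16.3 apply this to slit lamp and IOP.

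**Disease worsening.** Protocol 7.2.1.2.5: "Worsening of the underlying disease and/or of other pre-existing conditions will be recorded as an AE/SAE in the eCRF". Protocol 7.2.1.2.1 says that progression of the condition under study need not, by itself, be an adverse event unless it can reasonably be attributed to the study agent.

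**The concern.** ALK4290 is taken by mouth, so both eyes are exposed. The study eye must have active, previously untreated CNV (Protocol 5.1), and no other interventional therapy for wet AMD is allowed alongside (Protocol 6.4). Ocular events in that eye may therefore reflect the disease, the drug or both. Events in the fellow eye are useful context, above all because the trial has no control group (Protocol 10.1) and adverse events are its only secondary endpoint (Protocol 4.2, SAP 3.2).

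The planned tables put events from either eye into one count. A reader of the study report could not tell from them whether the ocular events sit almost wholly in the eye with CNV or also appear in the other eye. The SAP's own practice makes this stand out. Under SAP 16.2 a clinically significant slit-lamp finding is recorded as an AE, so the same finding is tabulated by eye as an examination result and loses its eye in the AE table.

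**Working it through.** The plan states no figure on this point, so the check is mainly a comparison of texts.

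**1. Do the general by-eye rules reach adverse events?**
- The by-eye sentence in SAP 16 concerns assessments. It stands in the paragraph on the other safety endpoints, after a separate sentence on how AEs are presented.
- SAP 9 makes the study eye the default for ocular assessments and efficacy measures, and says that fellow-eye data are listed and may be analyzed. AEs are not named.
- Neither rule prescribes a by-eye AE table, and no AE table title supplies one.

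**2. What does the counting rule do?** A preferred term counts once per subject. The same term in the study eye, in the fellow eye or in both adds one subject to the same row.

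**3. Can study-eye disease events enter these tables?** Yes under Protocol 7.2.1.2.5. Protocol 7.2.1.2.6 adds ophthalmic changes that the investigator judges clinically relevant. Under Protocol 7.2.1.2.1 some progression might not be recorded as an AE. The two rules lead to different table contents, so the mix of events is not fixed by the plan.

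**4. What can a pooled percentage tell the reader?** This is an illustration only. The per-eye incidences are assumed and the eyes are taken as independent. With study-eye incidence s and fellow-eye incidence f, the subject-level incidence is

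P = 1 − (1 − s)(1 − f).

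- Lowest assumed pair, s = 5%, f = 0%: P = 5%, or 1.5 of 30 subjects.
- Highest assumed pair, s = 30%, f = 10%: P = 1 − 0.70 × 0.90 = 37%, or 11.1 of 30.

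Fixing P at 20% (6 of 30) and solving s = 1 − 0.80/(1 − f):

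- f = 0%: s = 20%
- f = 5%: s = 1 − 0.80/0.95 = 15.8%
- f = 10%: s = 1 − 0.80/0.90 = 11.1%
- f = 20%: s = 0%

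One pooled figure thus fits anything from all events in the study eye to all events in the fellow eye. The same holds for a single preferred-term row, because each row is also counted without regard to eye.

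**The case against.** The other side has a good deal to say.

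- **The information is not lost.** A reader might infer that drug reactions and disease progression cannot be separated at all. The documents do not support that. Preferred-term rows may set a hemorrhage apart from a reaction of another kind. Table 14.3.3.1 shows ocular events suspected to be related. All AEs are listed and can be read by hand for about 30 subjects. Slit lamp and IOP are shown by eye, and fellow-eye BCVA is listed. This stands, with one reservation: relatedness is judged open-label, and both positive categories in Protocol 7.2.1.2.4 require a known response pattern, which a new ocular reaction may not fit.
- **The eye may already be collected.** A reader might infer from the item lists that the eCRF has no eye field. The eCRF is not among the documents, and the lists are not exhaustive: they omit the event term and the ocular/non-ocular flag on which the tables depend. Protocol 7.2.1.1 also asks for clarifying descriptions, which could carry the eye. This stands.
- **Pooling is inferred.** The SAP nowhere says that eyes are to be pooled. That follows from the absence of a split together with the counting rule. For the BCVA-loss AESI one could also argue that the SAP 9 study-eye default applies. The plan is unspecific here rather than committed to pooling.
- **The fellow eye is a weak comparator.** Protocol 5.1 requires that it too has no current or planned intravitreal anti-VEGF treatment, and SAP 4.1 foresees that both eyes may qualify. It need not be free of wet AMD. This stands and limits what a split can show.
- **No size can be put on the mixture.** A reader might infer that most pooled ocular events would be study-eye disease. The documents give no per-eye rates, so no such share can be derived.

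None of this supplies the eye in the five tables.

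**Conclusion.** The point holds in a limited form. As specified, the five ocular TEAE tables count subjects once per preferred term without distinguishing the eyes. They therefore cannot show whether ocular events cluster in the eye with active untreated CNV or also occur in the fellow eye exposed to the same oral drug. The SAP already follows a by-eye convention for slit lamp and IOP and does not extend it to adverse events.

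The effect is on interpretation only. Safety analyses are descriptive, so no sample size, error rate, analysis set or efficacy estimate changes. The illustration rests on assumed rates and independent eyes. It shows that the pooled figure is ambiguous and does not predict what will be seen. A split would not prove causation either, because the study eye carries both drug and disease and the fellow eye may be diseased. This is a cheap improvement to the reporting of the only secondary endpoint.

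**What to change.** 1. In SAP 16.1 and tables 14.3.2.1, 14.3.3.1, 14.3.4.1, 14.3.6.1 and 14.3.7.1, show ocular TEAEs in three columns: study eye, fellow eye, either eye. A subject with the same term in both eyes counts once in each column.
2. Present the BCVA-loss AESI in table 14.3.5 in the same way.
3. Show the eye in the AE listings (16.2.7.1 to 16.2.7.4).
4. Take the eye from the existing AE record. If it is not collected, obtain it by a query on the ocular terms already entered.
5. Reconcile Protocol 7.2.1.2.1 with 7.2.1.2.5 on whether worsening of the disease under study is recorded as an AE, and have the SAP follow the reconciled text.

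**Cost:** two extra columns per table and, at most, a query on ocular terms in about 30 subjects. The drawback is sparse cells, with many zeros and ones, so the columns should be read alongside the listings.

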16.2 Slit-Lamp Biomicroscopy Examination

Slit-lamp biomicroscopy examinations will be conducted on both eyes at all scheduled visits. The slit-lamp findings will include examinations of the cornea, conjunctiva, anterior chamber, iris/pupil, lens and

eyelids. Anterior chamber will be graded as +, ++, +++ or none; the other parameters will be graded as normal or abnormal. Abnormal findings will be further classified as not clinically significant (NCS) or clinically significant (CS). All clinically significant values will be recorded as AEs in the eCRF and followed until resolution. Once resolved, the AE eCRF page(s) will be updated

Slit-lamp findings will be summarized by visit, for the study eye and fellow eye separately, using qualitative summary statistics (frequency counts and percentages). Percentages will be based on the number of subjects with non-missing values at a given visit.

A shift table will show changes from baseline Visit 2 (Day 1) to all observations at later study visits. The data for slit-lamp biomicroscopy examinations will be presented in a listing.

16.3 Intraocular Pressure (IOP)

IOP will be measured using applanation Goldmann tonometry or equivalent tonometer in both eyes at all scheduled visits. IOP will be summarized for each eye (study eye and fellow eye) by visit using quantitative summary statistics. The number and percentage of subjects with IOP \geq 20 mmHg and the number and percentage of subjects with IOP \geq 30 mmHg will be summarized. Results will be listed for both eyes at each visit.

16.4 Clinical Laboratory Values

Blood samples and urine must be collected at every visit. Safety laboratory examinations will include hematology, biochemistry, coagulation, and qualitative urine analysis.

- Serology (screening only): hepatitis A (anti-immunoglobulin M (IgM), anti-IgM)), hepatitis B (hepatitis B antigen, anti-HBs, DNA), hepatitis C (anti-hepatitis C virus (HCV), ribonucleic acid (RNA) if anti-HCV positive), hepatitis D (anti-IgM, anti-immunoglobulin G (IgG)), hepatitis E (anti-hepatitis E virus (HEV), anti-HEV IgM, RNA if anti-HEV IgM positive), anti-smooth muscle antibody (titer), anti-nuclear antibody (titer), anti-liver-kidney microsomes (LKM) antibody, antimitochondrial antibody, Epstein Barr virus (vascularized composite allotransplantation (VCA) IgG, VCA IgM), cytomegalovirus (IgG, IgM), herpes simplex virus (IgG, IgM), varicella (IgG, IgM), parvovirus (IgG, IgM), toxoplasmosis (IgG, IgM)
- Hematology: hemoglobin, red blood cell count (RBC), white blood cell count (WBC) with differential, platelets
- Biochemistry: glucose, sodium, potassium, calcium, inorganic phosphate, creatinine, aspartate aminotransferase (AST), alanine aminotransferase (ALT), alkaline phosphatase (AP), lactate dehydrogenase (LDH), total bilirubin (if elevated provide direct bilirubin), urea, total protein, albumin, uric acid

- Coagulation: activated partial thromboplastic time (aPTT), prothrombin time (PT)/international normalized ratio (INR)
- Urine: potential of hydrogen (pH), glucose, erythrocytes, leukocytes, protein, nitrite and glomerular filtration rate (GFR)

All safety laboratory measurements will be performed at all scheduled visits by a central laboratory (except serology which is evaluated at screening only) . Investigators will get guidance and instructions on laboratory sampling and processing through a separate Lab Manual provided by the central laboratory.

The investigator is responsible for determining and documenting if out of range laboratory values are clinically significant or not. All clinically significant values will be recorded as AEs in the eCRF and followed until resolution. Once resolved, the AE eCRF page(s) will be updated.

Continuous biochemistry, hematology, and coagulation assessments will be summarized by visit and changes from baseline using quantitative summary statistics. The data for biochemistry and hematology will also be presented in listings.

Serology and urinalysis will be listed with collection information, and clinically significant findings, but no tabular summaries will be produced.

All laboratory values will be presented using conventional units.

